## 5 INVESTIGATIONAL PRODUCT

### 5.1 Dosing Form and Preparation

PRA023 concentrate for solution for infusion will be provided as a single-dose glass vial containing 500 mg of PRA023 at 60 mg/mL dose strength. PRA023 will be packaged in a box containing 6 vials per box. Each vial will contain at minimum 8.4 mL of PRA023. All study drug vials will indicate the lot number and the label affixed to the vial will contain the drug identification and conditions for storage. The vials do not contain antibacterial preservatives. Therefore, any unused portion of the study drug after single use should not be stored for reuse.

There are no matching placebo vials for this study. As such, the unblinded site pharmacist(s) or designee will need to prepare the study drug for infusion. Subjects randomized to placebo will receive normal saline infusions. Both the study drug and placebo infusion bags will be prepared in such manner that the Investigator and the subject will not know whether the subject is receiving PRA023 or placebo. Detailed study drug preparation and handling instructions will be provided in the Pharmacy Manual.

### 5.2 Storage

The study drug must be stored in a secure, lockable area in 36°F – 46°F (2°C – 8°C) controlled storage condition prior to use. All study drug must continue to be stored in a secure, lockable area until it is returned to the Sponsor or designee or destroyed upon approval by the Sponsor or designee.

### 5.3 Accountability

The study drug must be used in accordance with the protocol and only under the direction of the Investigator. The Investigator or designee shall keep and maintain complete and accurate records of all investigational materials. Records showing the receipt and disposition of all study drug shall include a master record listing the date of receipt of study drug shipment, the quantities received, and a dispensing record, which includes each quantity dispensed, identification of the person to whom dispensed, the date of dispensing, and the identification of the dispenser. The accountability records must be made available to the Sponsor's unblinded monitor or designee at any time.

At the termination of the study or at the request of the Sponsor or designee, the Investigator must return any unused study drug to the Sponsor or its designee according to applicable local and country regulations, and appropriately destroy any empty or used study drug vials. If return of unused study drug is not feasible, the Sponsor or designee will supply instructions as to how the supplies may be destroyed. All study drug supply destruction must be clearly documented. The Investigator must also provide a written explanation for any missing study drug.

## 5.4 Study Drug Administration

All doses of PRA023 or placebo will be administered intravenously as a 30-minute infusion using a calibrated infusion pump by the appropriately designated study staff at the investigational site.

Treatment of subjects with monoclonal antibodies may result in inappropriate immune responses and range from mild events with no apparent clinical manifestations to life-threatening or catastrophic reactions. Signs and symptoms of these events may develop during or shortly after infusion. As such, subjects must be closely monitored during administration of PRA023. Post-infusion observation period during the first 2 infusions (Week 0/Day 1 and Week 2) should be 1\* hour and subsequent infusions should be 30 minutes (Table 2, Table 3, and Table 4).

Some of the major safety concerns associated with immunogenicity are anaphylaxis, cytokine release syndrome, “infusion reactions”, and non-acute reactions such as delayed hypersensitivity; and manifestations may be common among these events.

The information below is provided as guidance to assess anaphylaxis, but the clinical judgment of the Investigator should be considered as well.

Anaphylaxis is a serious, acute allergic reaction characterized by certain clinical features. Signs and symptoms of anaphylaxis may include:

- Generalized hives, pruritis/itching, flushing, swollen lips/tongue/uvula
- Symptoms of respiratory compromise (e.g., dyspnea, wheeze/bronchospasm, stridor, reduced peak expiratory flow, hypoxemia)
- Reduced blood pressure (systolic blood pressure of less than 90 mm Hg or greater than 30% decrease from baseline) or associated symptoms of end-organ dysfunction (e.g., hypotonia [collapse], syncope, incontinence)
- Persistent gastrointestinal symptoms (e.g., crampy abdominal pain, vomiting)

If a subject experiences anaphylaxis, study drug administration should be discontinued immediately and permanently. If a subject experiences symptoms that may be attributed to hypersensitivity reaction or delayed hypersensitivity (e.g., fever, rash, arthralgia, myalgia, hematuria, proteinuria, serositis, central nervous system complications, or hemolytic anemia), study drug infusion should be stopped.

In the event that symptoms are mild or minor in severity, at the discretion of the Investigator, the infusion may be restarted at a slower rate if symptoms are resolved within 1 hour after the stop of infusion. If symptoms return, study drug should be discontinued immediately and permanently.

In the event that there is an infusion interruption, the entire duration of study drug infusion, from the initial start of infusion, to the completion of infusion, should not exceed 24 hours of PRA023 dilution. Subjects will receive appropriate treatment at the discretion of the Investigator.

---

\* 2 hours for subjects in Czech Republic

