**Table 2 Schedule of Study Assessments – Induction Period**

	Study Week	Study Visit							Early Termination	NOTES
		0	2	6	10	12	85			
	Study Day	1	15	43	71	85				
	Visit window (days)	0	±3	±3	±3	±3				
Procedure										
Eligibility Confirmation	X									
Randomization	X								Via IRT system	
Complete Physical Examination						X		X		
Targeted Physical Examination	X	X	X	X	X					
Vital Signs	X a	X	X	X	X	X a		X	Heart rate, temperature, blood pressure; Take pre-dose (no more than 30 minutes pre-infusion), end of infusion, and end of observation period a Weight needed	
ECG	X					X		X		
Adverse Events Assessment	X	X	X	X	X	X		X		
Concomitant Medication	X	X	X	X	X	X		X		
Efficacy Assessments										
Endoscopy with Biopsy						X		X	Endoscopy to be performed 7 or 6 days prior to or within +3 days after the Week 12 visit, or at the early termination visit. Refer to Section 6.4.2.	
Review eDiary Data from Subjects	X	X	X	X	X	X		X	Remind subjects to record in their eDiary daily	
Physician Global Assessment	X	X	X	X	X	X		X		
Partial Mayo Score		X	X	X	X				Include stool frequency, rectal bleeding, and physician's global assessment (PGA)	
Total Modified Mayo Score	X a					X		X	Include 4 components of stool frequency, rectal bleeding, endoscopy from Screening Period a , and PGA	
3-Component Modified Mayo Score	X a					X		X	Include 3 components of stool frequency, rectal bleeding, and endoscopy from Screening Period a	
IBDQ	X					X		X		
Laboratory Testing										
CBC	X		X			X		X		

	Study Visit							NOTES
	Study Week	0	2	6	10	12	Early Termination	
	Study Day	1	15	43	71	85		
Visit window (days)	0	±3	±3	±3	±3	±3		
Procedure								
Chemistry Panel	X		X			X	X	
Fasting Lipid Panel	X					X	X	
Urinalysis	X		X			X	X	
Urine Pregnancy Test (WOCBP only)	X		X			X	X	
Pharmacokinetics	X a	X b	X b	X b	X a	X	X	a. The PK samples at Week 0/Day 1 and Week 10 must be taken pre-dose, and immediately following the end of infusion (within 30 minutes) b. The PK sample taken at Weeks 2 and 6 must be taken pre-dose (within 30 minutes prior to dosing)

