Pharmacokinetic Sub-Study (Optional)	X a				X a			a. In addition to the PK samples obtained in all subjects, PK sub-study subjects will have the following samples obtained: Week 0/Day 1 and Week 10: 4 days (96±5 hours) and 1 week (168±5 hours) after completion of infusion. Refer to Section 6.6.1 for additional details.
Immunogenicity	X	X	X	X		X	X	To be taken pre-infusion.
Biomarkers								
Biomarkers	X	X	X	X	X	X	X	Serum at all visits; additional whole blood at Weeks 0, 6, and 12
Soluble TL1A	X	X	X	X	X	X	X	
hsCRP	X	X	X	X	X	X	X	
Fecal Calprotectin	X			X		X	X	
Infusion	X	X	X	X	X			Include date, start and stop time, volume infused, and length of the IV infusion. Observation period at Week 0/Day 1 and Week 2 will be 1 hour (2 hours for subjects in Czech Republic); 30 minutes for all subsequent infusions thereafter.

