**Table 3 Schedule of Study Assessments – Open-Label Extension Period for 1st Induction Responders**

	Study Visit										NOTES	
	Study Week	14	18	26	34	42	50	Quarterly (Q12w)* Office Visits after Week 50	Early Termination	Infusion Visits (excluding Office Visits)		
Study Day	99	127	183	239	295	351						Note: Subjects who are responders after the First Induction Period proceed to re-randomization at Week 14 *Weeks 62, 74, 86, 98, 110, 122, 134, 146, 158, and 170
Visit window (days)	±7	±7	±14	±14	±14	±14	±14					
Procedure												
Enter subject into IRT for OLE	X											
Complete Physical Examination						X		X a	X			a. Yearly after week 50
Targeted Physical Examination	X	X	X	X	X			X a				a. Except when the yearly complete exam is done
Vital Signs	X	X	X a	X	X	X a	X a		X a	X		Heart rate, temperature, blood pressure; Take pre-dose (no more than 30 minutes pre-infusion) and end of infusion a. Weight needed
EKG			X			X			X			
Adverse Events Assessment	X	X	X	X	X	X	X	X	X	X		
Concomitant Medication	X	X	X	X	X	X	X	X	X	X		
Efficacy Assessments												
Review Diary Data from Subjects	X	X	X	X	X	X	X	X	X	X		Electronic or paper diaries may be used
Physician Global Assessment	X	X	X	X	X	X	X	X	X	X		
Partial Mayo Score	X	X	X	X	X	X	X	X	X	X		Include stool frequency, rectal bleeding, and physician's global assessment (PGA)
Total Modified Mayo Score								X a	X	X		Include 4 components of stool frequency, rectal bleeding, endoscopy, and PGA a. Only if endoscopy is performed
3-component Modified Mayo Score								X a	X	X		Include 3 components of stool frequency, rectal bleeding, and endoscopy a. Only if endoscopy is performed
Endoscopy with Biopsy								X ab	X c	X c		Endoscopy can be performed 14 to 6 days prior to Week 50 and Week 98 visits or within 7 days after Week 50, Week 98, or ET visit

	Study Visit										NOTES	
	14	18	26	34	42	50	Quarterly (Q12w)* Office Visits after Week 50	Early Termination	Infusion Visits (excluding Office Visits)			

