Study Week	14	18	26	34	42	50						Note: Subjects who are responders after the First Induction Period proceed to re-randomization at Week 14 *Weeks 62, 74, 86, 98, 110, 122, 134, 146, 158, and 170  a. For subjects who have had a diagnosis of UC for $\geq 7$ years and have been treated in OLE, the Week 50 and Week 98 endoscopies should also be a malignancy surveillance colonoscopy (rather than sigmoidoscopy). Refer to Section 6.4.2. b. Done annually (11-13 months from prior endoscopy) c. Required if $>3$ months since prior endoscopy  a. Every 6 months
Study Day	99	127	183	239	295	351	$\pm 14$			$\pm 7/\pm 14$		
Visit window (days)	$\pm 7$	$\pm 7$	$\pm 14$	$\pm 14$	$\pm 14$	$\pm 14$						
Procedure												
IBDQ			X			X	X a		X			
Laboratory Testing												
CBC	X	X	X	X	X	X	X		X			
Chemistry Panel	X	X	X	X	X	X	X		X			
Fasting Lipid Panel			X			X	X a		X			a. Every 6 months
Urinalysis	X	X	X	X	X	X	X a		X			a. Every 6 months
Urine Pregnancy Test (WOCBP only)	X	X	X	X	X	X	X		X			Pregnancy testing must be done once a month
Pharmacokinetics	X a		X a		X a	X a	X b		X			a. To be taken pre-infusion b. To be taken pre-infusion; every 6 months
Immunogenicity			X a		X a	X a	X b		X			a. To be taken pre-infusion b. To be taken pre-infusion; every 6 months
Biomarkers												
Biomarkers	X	X	X	X	X	X	X a		X			Additional whole blood at Week 50 and Week 98 a. Every 6 months
Soluble TL1A	X	X	X	X	X	X			X			
hsCRP	X	X	X	X	X	X	X a		X			a. Every 6 months
Fecal Calprotectin			X	X	X	X	X a		X			a. Every 6 months

	Study Visit										NOTES	
	14	18	26	34	42	50	Quarterly (Q12w)* Office Visits after Week 50	Early Termination	Infusion Visits (excluding Office Visits)			
Study Week	14	18	26	34	42	50						Note: Subjects who are responders after the First Induction Period proceed to re-randomization at Week 14 *Weeks 62, 74, 86, 98, 110, 122, 134, 146, 158, and 170
Study Day	99	127	183	239	295	351						
Visit window (days)	±7	±7	±14	±14	±14	±14	±14		±7/±14			
Procedure												
Infusion	X	X	X	X	X	X	X		X a			a Q4 week infusion visits Include date, start and stop time, volume infused, and length of the IV infusion Infusion observation period will be 30 minutes

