### 8.3 Evaluation of Safety Variables

Data will be summarized with respect to safety observations. Monitoring of AEs, physical examinations, vital signs, ECGs, safety and tolerability monitoring evaluations, clinical laboratory evaluations, and special procedures are detailed in [Section 6.3](#).

All available safety data for all randomized subjects who receive at least one dose of PRA023 will be included in the safety analysis, which will be primarily descriptive.

The safety variables will be:

- Hematology, chemistry, coagulation, and urinalysis
- Vital signs
- ECG parameters

- Physical examination
- AEs and SAEs
  - AEs of special interest: infections, acute infusion reaction (within 1 hour of completion of infusion), and peri-infusion reaction (within 24 hours of completion of infusion)
  - AEs in subjects who are ADA positive

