#### **9.3.7.1 Adverse Events and Adverse Events of Special Interest**

All AEs will be coded using most current version of Medical Dictionary for Regulatory Activities (MedDRA). All reported adverse events will be assigned to the SOC and PT according to MedDRA. The number and percentage of subjects reporting adverse events (all, serious, related) will be tabulated by overall and treatment. AEs will be summarized by SOC and PT. AEs will also be summarized by relationship to the study drug, seriousness and severity.

A treatment-emergent AE (TEAE) will be defined as an AE that began or worsened on or after the first treatment dose. AEs recorded prior to the first infusion of study treatment will be considered non-treatment-emergent.

All reported AEs (treatment-emergent or not) will be listed. Only TEAEs will be summarized.

AEs of special interest including infections, acute infusion reaction (within 1 hour of completion of infusion), and peri-infusion reaction (within 24 hours of completion of infusion) will be summarized based on a pre-specified MedDRA list.

AEs occurring in subjects who are considered immunogenicity positive will also be summarized.

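### The longer post-infusion observation and the end-of-observation vital signs are tied to induction visits and not repeated at OLE entry, so former placebo subjects get their first two PRA023 infusions with 30 minutes of scheduled observation

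*Protocol*

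**What the plan says.** Two rules in the Protocol govern monitoring after an infusion.

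- **Length of observation.** Section 5.4: "Post-infusion observation period during the first 2 infusions (Week 0/Day 1 and Week 2) should be" 1 hour, with a footnote giving 2 hours in the Czech Republic. Later infusions get 30 minutes, and the text cites Tables 2, 3 and 4 for this. Table 2 agrees: "Observation period at Week 0/Day 1 and Week 2 will be 1 hour (2 hours for subjects in Czech Republic"). Table 3, for OLE subjects who responded to the first induction, says "Infusion observation period will be 30 minutes". Table 4, for non-responders, has the same wording. Neither OLE table makes an exception for Weeks 14, 16 or 18, or for the Czech Republic.
- **Vital signs.** Table 2, for induction visits: "Take pre-dose (no more than 30 minutes pre-infusion), end of infusion, and end of observation period". Tables 3 and 4, for OLE visits: "Take pre-dose (no more than 30 minutes pre-infusion) and end of infusion".

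On exposure, Section 5.1 says: "Subjects randomized to placebo will receive normal saline infusions". Section 4.1 lets subjects who complete induction in either cohort enter the OLE. From Week 14, non-responders receive 1000 mg and then 500 mg at Weeks 16, 20 and 24. Responders receive 250 mg or 100 mg every 4 weeks. Section 1.4.2 confirms that some subjects had about 3 months of placebo followed by PRA023.

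**The concern.** The longer observation is attached to two calendar visits. For the active arm these are the first two exposures to the antibody. For the placebo arm they are two saline infusions. When placebo subjects do meet the antibody, the longer period has lapsed and the last scheduled vital signs are at end of infusion.

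Section 5.4 warns that reactions to a monoclonal antibody range up to life-threatening and may appear during an infusion or soon after it. A non-responder from the placebo arm starts with the same 1000 mg load that earned 1 hour at Week 0. Section 1.5 expects that load to give the highest concentration in the regimen. What is at stake is the monitoring of these subjects at first exposure and, to a lesser degree, how OLE infusion reactions are read against those seen in induction.

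**Working it through.** There is no plan figure to reproduce. The check sets the schedules side by side and then counts the subjects concerned.

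**Schedule at the first two PRA023 infusions**

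| | Active arm | Former placebo, non-responder | Former placebo, responder |
|---|---|---|---|
| Visits | Weeks 0 and 2 | Weeks 14 and 16 | Weeks 14 and 18 |
| Doses | 1000 mg, 500 mg | 1000 mg, 500 mg | 250 or 100 mg each |
| Source | Section 5.4, Table 2 | Table 4 | Table 3 |
| Observation | 2 × 60 = 120 min | 2 × 30 = 60 min | 2 × 30 = 60 min |
| Czech Republic | 2 × 120 = 240 min | 60 min | 60 min |
| Vital-sign sets | 2 × 3 = 6 | 2 × 2 = 4 | 2 × 2 = 4 |

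Ratio of scheduled observation: 60/120 = one half; Czech Republic 60/240 = one quarter.

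**Could the text be read as the first two PRA023 infusions?** No. Section 5.4 names the weeks and cites Tables 3 and 4 for the 30 minutes. Section 6 adds that the schedule tables prevail over the text. Text and tables agree with each other, so this is a gap in the design and not an inconsistency.

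**Subjects concerned over the whole trial.** Inputs: 120 in Cohort 1 and up to 50 in Cohort 2 (Protocol Section 8.2); 48 in Cohort 2 (SAP addendum Section 3.1); 1:1 allocation (Protocol Section 8.1).

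- (120 + 48)/2 = 84 placebo subjects; at the ceiling, 170/2 = 85.
- OLE entry is optional and no rate is given. If 70% to 100% enter (assumption), 0.70 × 84 = 59 up to 84.

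**Subjects with Week 14 still ahead at version 5.0**

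- The interim review of 19 October 2022 was planned for about 96 Cohort 1 subjects at Week 12 or terminated, so about 96/2 = 48 of the 60 placebo subjects in that cohort.
- Not accounted for then: 84 − 48 = 36 (12 from Cohort 1, 24 from Cohort 2).
- Version 5.0 is dated 14 June 2023, 238 days (34 weeks) later. Week 14 is Day 99, so only subjects randomized after about 8 March 2023 (98 days earlier; visit window ±7 days) would still face it.
- From 19 October 2022 to 8 March 2023 is 140 days, or 20 weeks. Anyone randomized in that time, or before it and still short of Week 12 at the review, comes off the 36.

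The documents give no enrollment dates, so the remaining number cannot be calculated.

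**The case against.** The best case against acting has five parts.

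- **Few or no subjects may be left to benefit.** This stands. A reader might take 36 as the number who could still be helped. The documents do not support that. It would need every remaining Cohort 1 placebo subject and every Cohort 2 placebo subject to have been randomized after about 8 March 2023. Section 4.1 lets Cohort 2 enrollment start once any Cohort 1 stratification limit is reached, and the SAP addendum reports a recommendation to continue that enrollment. Cohort 2 was therefore apparently already enrolling in October 2022.
- **The acute-reaction window is not an observation standard.** Section 8.3 lists as an adverse event of special interest "acute infusion reaction (within 1 hour of completion of infusion"). A reader might infer that crossovers alone are observed for only half of that hour. In fact the window classifies events, and active-arm subjects at Weeks 6 and 10 are also observed for 30 minutes. The window is context, not the main argument.
- **Other safeguards apply.** Section 5.4 asks for close monitoring during administration and sets stopping rules. Section 6.2 allows unscheduled procedures for subject safety, and nothing forbids a longer stay. Adverse events are recorded until 84 days after the last dose, so it would be wrong to infer that a late reaction goes unrecorded. All this reduces the weight of the point, but none of it requires longer observation after a first PRA023 infusion.
- **No safety signal is documented.** Phase 1 gave up to 1000 mg once and 500 mg repeatedly, with no serious or severe events (Section 1.4.2). The data monitoring committee recommended continuing. This limits the concern but does not explain why the two arms are treated differently at first exposure.
- **The rationale is inferred.** The Protocol does not say why the period falls to 30 minutes. That first exposure is the reason for the longer period is a natural reading of Section 5.4, but only a reading.

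**Conclusion.** The gap is real and modest: a cheap improvement. At their first two PRA023 infusions, former placebo subjects have half the scheduled observation of the active arm (a quarter in the Czech Republic) and no vital signs at the end of it.

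Up to 84 or 85 subjects are concerned over the whole trial, or 59 to 84 if 70% to 100% enter the OLE. For those already past Week 14, it is an assumption that protocol versions before 5.0, which are not available, had the same 30-minute rule. The number still short of Week 14 at version 5.0 is unknown, probably small and possibly zero. No reaction rate is given, so the number of events affected cannot be estimated.

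The randomized 12-week comparison, alpha and power are untouched.

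**What to change.** Add a footnote to Section 5.4 and to Tables 3 and 4. It should apply the Week 0/2 observation period (including the Czech 2 hours) and the end-of-observation vital signs at the first two OLE infusions: Weeks 14 and 18 in Table 3, Weeks 14 and 16 in Table 4. It should cover every OLE entrant. A longer visit for former placebo subjects alone would reveal induction assignment, and Section 4.1.4.3 restricts breaking the code to individual adverse events that cannot be treated without it.

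If no placebo subject still has Week 14 ahead, no amendment is needed. A note on the shorter scheduled observation, placed where OLE infusion-reaction events of special interest are reported, is then enough. First exposures that took place under the 30-minute rule need that note in either case.

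Cost per entrant: up to 2 × 30 = 60 extra minutes (2 × 90 = 180 in the Czech Republic) and two extra vital-sign sets. Former active-arm subjects, who may already have had four PRA023 infusions, bear this too. No new type of procedure is involved. Section 10.5 requires ethics approval of any amendment before it takes effect, so the change is best bundled with another amendment. The time that approval takes further reduces the number who could benefit.

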## 6 STUDY PROCEDURES

A schedule of study procedures is presented in [Section 6.1.1](#). If any discrepancies should be found between the text of the protocol and the Schedule of Study Assessments tables, the tables will predominate.

Every effort should be made to ensure that the protocol-required tests and procedures are completed as described. However, it is anticipated that from time to time there may be circumstances, outside of the control of the Investigator that may make it unfeasible to perform the test. In these cases, the Investigator will take all steps necessary to ensure the safety and well-being of the subject. When a protocol-required test cannot be performed, the Investigator will document the reason for this and any corrective and preventive actions that he or she has taken to ensure that normal processes are adhered to as soon as possible. The Sponsor or designee will be informed of these incidents in a timely fashion.

